#### 8.2.10. Antibiotics for the treatment of any kind of infection

The following information will be summarized for antibiotic treatment of any kind of infection between day 1 and week 51/52:

- Percentage of patients taking at least an antibiotics for treatment of infections
- Estimate of mean and SD of the incidence rate by the simple estimator
- Duration on antibiotics for the treatment of any kind of infection
- The estimate and 1-sided 99% upper confidence limit using Poisson model.

The length of the observation period after the start of treatment per patient will be used as offset in the Poisson model. The unit of measurements of time is years.

Definition of incidence rate is given in [Section 8.1.1](#).

Computation of the estimate and 1-sided 99% upper confidence limit using Poisson model is given in [Section 8.1.2](#).

Computation of the simple estimator is given in [Section 8.1.3](#).

Definition of duration of antibiotics for the treatment of any kind of infection is given in [Section 6.2.9](#).

In addition, the number and percentage of patients taking concomitant antibiotic medications will be summarized by ATC Levels 2, 3 and 4.

#### 8.2.11. Days of missed work/school/other major activities due to infections

The following information will be summarized for missed work/school/other major activities due to infections between day 1 and week 51/52:

- Total days of missed work/school/other major activities due to infections

#### 8.2.12. Pediatric Quality of Life Inventory (PedsQL™) (Generic Core Scales)

For the analysis of PedsQL™ (4) three scores will be calculated:

- Total Scale Score (all 23 items)
- Physical Health Summary (8 items)
- Psychosocial Health Summary (15 items)

The parent proxy-report for children aged 2-4 years consists of 21 items.

The following information will be summarized at baseline, week 24 and at the study termination visit (week 51/52) for the summary scores and the single dimension scores (physical functioning, emotional functioning, social functioning, school functioning) by age group (2-4 years, 5-7 years, 8-12 years, 13-18 years, 18-25 years, >25 years):

- Actual value, change from baseline and relative change from baseline

Both child self-reports and parent proxy-reports will be presented, if applicable.

Scoring and handling of missing values will be done as recommended in the user manual.

This document is confidential.

CCI

This document is confidential.

## 9. Pharmacokinetic Evaluation

The PK analyses will be performed using PK evaluation set.

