
Sponsor Name: Kedrion S.p.A. - [name]	
Product Name: NA	Investigational Product: Kedrion intravenous immunoglobulin (IVIg) 10%
Study Procedures: 
At the screening visit, the signed ICF and authorization to access personal health information will be obtained from the patient or the patient's parent(s)/legal guardian(s). The assent form will be also collected for children, as applicable according to local regulation.
 
Screening procedures will be performed up to 21 or 28 days (depending on the treatment regimen) prior to the first Klg10 infusion. During the screening, the diagnosis of PID will be confirmed by the site Investigator.
 
Each patient will be treated with the investigational product at a dose of 200 to 800 mg/kg body weight every 21 or 28 days for a period of 48 weeks (see protocol Time and Events table).
 
A blood sample will be obtained from all patients for evaluation IgG trough levels at screening, before each infusion, every 21 or 28 days during all study periods, and at the study termination visit.
 
Blood samples required for PK analysis will be taken before and after the 5th study infusion (for 28-day infusion schedule) and the 7th study infusion (for 21-day infusion schedule) for those patients that consent to the PK portion of the study.
 
A pretreatment serum sample at the screening visit and a serum sample at the study termination visit will be collected and stored at <math>\leq -70^{\circ}\text{C}</math> for viral safety and possible future testing.
 
A Patient Diary will be given to the patient at each infusion visit. The patient and/or patient's parent(s)/guardian(s) will be trained by the Investigator on how to complete the Patient Diary, starting after the first infusion. The Patient Diary will be collected at the following visit, data will be reviewed by the Investigator, and a new Patient Diary will be provided to the patient.
 
The patient will be asked to complete QoL questionnaires (general and specific) at 3 visits as follows: at baseline (prior to first infusion of Klg10), at week 24 of treatment (infusion 7 for the 28-day schedule or infusion 9 for the 21-day schedule), and at the study termination visit. Patients who are unable to independently complete the questionnaires may enlist the assistance of a parent or caregiver.
 
During the study [at week 24 (infusion 7 for the 28-day schedule or infusion 9 for the 21-day schedule)] the patient will be asked to complete short assessment questionnaire (Appendix A to the protocol) about personal satisfaction with participation and treatment during the study.
	

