**Investigational Product:**

Kedrion intravenous immunoglobulin (IVIg) 10%

years. The estimate and 1-sided 99% upper confidence limit will be reported. Efficacy will be claimed if this limit is less than 1.0. Supportive and sensitivity analyses will be performed as appropriate. Secondary and exploratory efficacy endpoints will be summarized using descriptive statistics.

Secondary safety endpoints will be summarized using descriptive statistics.

Additionally, a 1-sided 95% confidence interval (CI) will be produced for the proportion of infusions with 1 or more temporally-associated AEs (including AEs determined not to be product-related) using an exact binomial method. Due to the clustered nature of the data, a Design Effect will be applied to the CI. An analysis of variance method will be used to calculate the Intra Cluster Correlation Coefficient (Wu, 2012). For this analysis, safety will be declared if the upper 1-sided 95% confidence is less than **CCI**. Other methods that take in account the clustered nature of the data could be performed (e.g., Generalized Estimating Equation).

Further details will be provided in the SAP.

Pharmacokinetic analysis of total IgG, IgG subclasses, and selected specific IgG antibody levels will be done by non-compartmental analysis. Pharmacokinetic parameters will be derived from serum IgG levels and summarized descriptively, taking into account doses of the drug. Trough levels for all patients will be summarized relative to dosing interval and age category. The frequency of patients with trough concentrations < 6 g/L will be estimated for each infusion number, dose level, and age category, as well as overall. All other data will be reported descriptively. Trough concentrations for total IgG at steady state achieved by the study drug will be compared to IVIg trough concentrations prior to the study entry using statistical model.

Interim PK analysis will be performed when approximately **CCI** adult patients (in order to have 20 evaluable patients) complete intense PK sampling before and after infusion 5 for the 28-day schedule and infusion 7 for the 21-day schedule.

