#### 5. SELECTION OF STUDY POPULATION

The study will entail the evaluation of approximately 50 patients selected in accordance with both the FDA and EMA guidelines stated previously, except for the pediatric enrollment being lower than that required by FDA and EMA for market approval.

Patients with a confirmed diagnosis of PID will be selected for the study. Confirmation of PID diagnosis will include a review of infections history, trough IgG serum concentration within 12 months (at least 2 documented IgG trough levels, 1 must be within 6 months), and previous IVIg treatment data (last 3 commercially available IVIg infusions administered before study entry).

Up to 12 pediatric patients (2 to 17 years old) may be enrolled among the 50 patients to gain primary data for the full pediatric study which is deferred after Biologic License Application approval of the PID adult population. In the meantime, enrollment of the 2 to 11 year old pediatric patients in this study will be delayed until acceptable safety and efficacy of Klg10 for the PID treatment of adolescent or adult patients are demonstrated.

Patients who have an acute infection at the time of screening (exclusion criterion #8) may be rescreened at the investigator's discretion as long as the infection is not serious and is resolved by the time of rescreening.

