## 8.4 PHARMACOKINETIC ASSESSMENT (PK EVALUATION SET)

Pharmacokinetic assessments will be performed in approximately 24 adult patients in order to have 20 evaluable patients before and after the 5th study infusion (28-day infusion schedule) or the 7th study infusion (21-day treatment schedule), when steady state is expected to be achieved (after 5 half-lives of regular infusion of the IMP). Interim PK analysis will be performed when approximately 24 adult patients (20 evaluable patients) complete intense PK sampling before and after infusion 5 for the 28-day schedule or infusion 7 for 21-day schedule.

Blood samples (approximately 20 mL) will be obtained at the following time-points:

- 30 minutes to 10 minutes pre-infusion
- 30 minutes ( $\pm$  5 minutes) post-infusion
- 2 hours ( $\pm$  15 minutes) post-infusion
- 24 hours ( $\pm$  2 hours) post-infusion
- 72 hours ( $\pm$  2 hours) post-infusion
- 7 days ( $\pm$  1 day) post-infusion
- 14 days ( $\pm$  1 day) post-infusion
- 21 days ( $\pm$  1 day) post-infusion
- 28 days ( $\pm$  2 days) post-infusion (only for 28 days treatment schedule)

Information about the PK assessment will be recorded in the source documentation at the study site and in the eCRF.

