### 10.1 ANALYSIS SETS

The efficacy and safety analyses will be based, respectively on the Full Analysis Set (FAS) and the Safety Set (SAF) unless stated otherwise. All PK analyses will be done on the PK Evaluation Set.

The following analysis sets will be defined:

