### 5.4. Pharmacokinetic (PK) Evaluation Set

The PK Evaluation Set includes all adult patients that consent to this part of the protocol and who have PK analysis performed at the 5th infusion (28-day infusion schedule) or the 7th infusion (21-day infusion schedule). The population includes all patients following the principles of the SAF for whom at least 1 concentration of total IgGs, IgG subclasses 1-4, or IgG specific antibody levels (anti-haemophilus influenza type b, anti-tetanus toxoid, anti-pneumococcal capsular polysaccharide), measured in the dense sampling period (i.e., before and after the 5th infusion of the 28-day infusion schedule and before and after the 7th infusion for the 21-day infusion schedule).

PK concentrations are listed for all patients in the PK Evaluation Set.

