#### 9.6. Comparison of Total IgG trough concentrations

The evaluation of trough concentrations of Total IgG during the study compared to IVIg trough concentrations prior to the study entry will be carried out descriptively, separately for each dosing schedule.

The Total IgG trough concentrations prior to study entry will be compared to the mean of steady state trough concentrations as defined in previous section.

The comparison will be explored graphically using box plots for both dosing schedules separately.

This document is confidential.

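### As far as the visible text shows, the comparison of pre-study IVIg troughs with steady-state KIg10 troughs (SAP 9.6) is confined to about 24 consenting adults, although both troughs are available for every patient

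*SAP*

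**What the plan says.** **Analysis set.** SAP Section 9 states: "The PK analyses will be performed using PK evaluation set". Protocol 10.1 gives the same rule: "All PK analyses will be done on the PK Evaluation Set". SAP 5.4 defines membership: "The PK Evaluation Set includes all adult patients that consent to this part of the protocol", with the further condition of PK sampling at infusion 5 (28-day schedule) or infusion 7 (21-day schedule). Protocol 8.4 gives the size: "Pharmacokinetic assessments will be performed in approximately 24 adult patients in order to have 20 evaluable patients".

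**The comparison.** SAP 9.6 says: "The Total IgG trough concentrations prior to study entry will be compared to the mean of steady state trough concentrations". It is descriptive, separate for each dosing schedule and shown with box plots. The visible text of 9.6 names no analysis set and takes its definition of steady state from the preceding section, which is blacked out.

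**The objective.** The pharmacokinetic objective (Protocol 3.1, SAP 3.1.3) has two sentences. The first, on distribution, metabolism and elimination, is limited to 20 adults. The second, on comparing troughs with those before study entry, has no such limit.

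**The data.** The Protocol synopsis says: "A blood sample will be obtained from all patients for evaluation IgG trough levels at screening, before each infusion". Inclusion criterion 5 requires every patient to have at least two documented pre-study troughs of 6 g/L or more. The synopsis also says: "Trough levels for all patients will be summarized relative to dosing interval and age category". SAP 8.2.1 summarises on-study troughs on the FAS.

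**The concern.** Nothing in the comparison needs the intensive profile. It needs a documented pre-study trough and pre-infusion values at steady state, and the protocol secures both for every patient. The restriction appears to come from where 9.6 is placed, since no visible text justifies it for troughs. The list of endpoints reserved for the PK Evaluation Set (Protocol 10.4.4, SAP 4.4) does not include the pre-study comparison. The reason given for leaving age categories out of PK (Protocol 10.6.1, SAP 6.6.1) is that blood is taken only from adults. That is true of the intensive samples but not of troughs.

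A programmer who follows the visible SAP would run 9.6 on the smaller set. A stated objective would then be answered in about half the patients, selected by willingness to undergo intensive sampling, with no child or adolescent among them. The box plots by schedule would divide that number again.

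**Working it through.** The documents give no power or precision for this comparison, so there is no figure of the plan's own to reproduce. The check is a count of patients, followed by the effect of that count on a standard error.

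**Inputs**
- Total: "The study will entail the evaluation of approximately 50 patients" (Protocol Section 5). SAP 3.6 speaks of about 50 screened, allowing 10% for screening failures and 10% for dropouts, with 40 evaluable.
- PK Evaluation Set: about 24 adults, 20 evaluable (Protocol 8.4).
- Paediatric patients: up to 12 of the 50 (Protocol Section 5).

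**Step 1: patients who could enter the comparison.** With 50 screened, 50 × 0.90 = 45 are treated. Taking off both allowances, 50 × 0.80 = 40, which agrees with the plan's evaluable number. If the 50 are read as treated patients, as Protocol Section 5 may suggest, the total is 50.

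**Step 2: patients left out.** Share left out = 1 − n(PK set) / n(total).
- Treated, 50 screened: 45 − 24 = 21; 21/45 = 47%.
- Evaluable against evaluable: 40 − 20 = 20; 20/40 = 50%.
- Treated, if all 50 are treated: 50 − 24 = 26; 26/50 = 52%.

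All patients under 18 are left out by definition, up to 12. With 12 among 50 there are 38 adults, so 38 − 24 = 14 adults are left out as well.

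**Step 3: effect on the standard error of a mean difference.** At equal SD, the ratio (smaller set to larger set) is √(n total / n PK set).
- √(45/24) = 1.37
- √(40/20) = 1.41
- √(50/24) = 1.44

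**Step 4: what SAP 8.2.1 supplies instead.**
- *Set.* 8.2.1 uses the FAS, by age category, by schedule and overall (SAP 8 and 8.2). 9.6 uses the PK Evaluation Set, by schedule only.
- *Reference value.* 8.2.1 uses the last valid value before the first infusion (SAP 6.2.2), normally Day 1. 9.6 uses the pre-study troughs.
- *On-study value.* 8.2.1 reports each visit separately. 9.6 uses the mean of the steady-state troughs.
- *Pre-study troughs on the FAS.* SAP 7.4 reports how many were at or above 6 g/L, together with baseline IgG. It does not plan a summary of the pre-study values themselves.

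So 8.2.1 comes close to the comparison in 9.6 without being the same one.

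**The case against.** Four points on the other side deserve weight.

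**The section before 9.6 is redacted.** It defines the steady-state trough and could name a population. This stands: the finding covers only the visible text and is conditional on that section.

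**SAP 8.2.1 already covers most of the ground.** Patients enter after at least three cycles of commercial IVIg, so the Day 1 pre-infusion value reflects the previous product. Change from baseline is then, in substance, a comparison of KIg10 with prior IVIg in all treated patients, children included. This largely stands. A reader might infer that half the trough data and all paediatric patients drop out of the trough evidence. The documents do not support that; the loss is confined to 9.6. What 8.2.1 does not give is the contrast with the documented pre-study troughs or with the steady-state mean.

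**The synopsis does not contradict the SAP.** A reader might take its sentence on all patients as assigning the comparison to everyone. That sentence concerns trough summaries, which 8.2.1 delivers. The later sentence on the comparison names no set, and no text promises age categories for it.

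**The comparison is descriptive.** SAP 9.6 plans no interval, test or decision rule, so confidence-interval widths in g/L would need an assumed SD and would describe an output the SAP does not contain. This stands, and the size is given here only as patient counts and a ratio. The synopsis does mention a statistical model for this comparison; that is a separate discrepancy.

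One could add that the pre-study troughs may be up to 12 months old and were selected by a threshold, so the Day 1 value may be the better reference. That limits what 9.6 can show in either set. It is no reason to run it in fewer patients.

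**Conclusion.** The point holds for the comparison in SAP 9.6 and no further. On the visible text, this objective is addressed in about 24 consenting adults (20 evaluable) where about 45 treated (40 evaluable) could contribute. Between 47% and 52% of patients are left out, including all of the up to 12 under 18. Using every patient with both troughs would make the standard error about 1.4 times smaller.

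This rests on three assumptions: the planned numbers are met, the SD is the same in both sets, and the redacted section names no other set. Patients who leave before steady state would not contribute, so the realised number may be nearer 40 than 45.

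It is worth correcting because it improves both precision and representativeness without further data collection. It is moderate in weight, because 8.2.1 supplies related evidence on the FAS and no efficacy or safety conclusion depends on 9.6.

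**What to change.** First check whether the redacted section before 9.6 already names a set. If it does not:

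- State in SAP 9.6, and for the trough displays in 9.4.3 and 9.4.4, that the analysis uses all FAS patients with at least one documented pre-study trough and at least one steady-state pre-infusion trough, as the SAP already defines steady state. Present it by schedule, with age category shown.
- Keep the PK Evaluation Set for the intensive-profile parameters, and show the 9.6 result in that set as a supportive subset.
- Add the exception to the sentence in Protocol 10.1 that assigns all PK analyses to the PK Evaluation Set.

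The cost is a few sentences and one rerun of the planned programs on a larger set. No new samples or visits are needed, and the intensive PK parameters are unaffected.

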### 9.1. PK sampling Schedule

Pharmacokinetic assessments will be performed in approximately [REDACTED] adult patients in order to have 20 evaluable patients before and after the 5th study infusion (28-day infusion schedule) or the 7th study infusion (21-day treatment schedule), when steady state is expected to be achieved (after 5 half-lives of regular infusion of the IMP). Interim PK analysis will be performed when approximately [REDACTED] adult patients (20 evaluable patients) complete intense PK sampling before and after infusion 5 for the 28-day schedule or infusion 7 for 21-day schedule.

Blood samples (approximately 20 mL) will be obtained at the following time-points at 5th (28-day schedule) or 7th (21-day schedule) study infusion:

- 30 minutes to 10 minutes pre-infusion
- 30 minutes ( $\pm$  5 minutes) post-infusion
- 2 hours ( $\pm$  15 minutes) post-infusion
- 24 hours ( $\pm$  2 hours) post-infusion
- 72 hours ( $\pm$  2 hours) post-infusion
- 7 days ( $\pm$  1 day) post-infusion
- 14 days ( $\pm$  1 day) post-infusion
- 21 days ( $\pm$  1 day) post-infusion
- 28 days ( $\pm$  2 days) post-infusion (only for 28 days treatment schedule)

### 9.2. PK Parameters

Non-compartmental PK parameters will be calculated using Phoenix WinNonlin 8.0 or higher version. Actual sampling times will be used in the determination of the individual PK parameters. Linear up log down method will be used for derivation of AUC.

#### 9.2.1. Total IgG PK

Total IgG levels will be listed individually by time point, and serum concentration-time curve (individually and mean $\pm$ SD) will be plotted. The serum levels will be presented in g/L units.

Following PK parameters will be evaluated:

- $T_{1/2}$ ,  $AUC_{0-t}$ ,  $AUC_{0-inf}$ ,  $AUC_{tau}$ ,  $V_d$ ,  $CL_{ss}$ ,  $C_{max}$ ,  $C_{min}$ ,  $T_{max}$ , and  $K_{el}$ ,  $C_{avg}$  and % Fluctuation

$AUC_{0-inf}$  will be evaluated if data meet PK acceptance criteria to elimination parameters; AUC over dosing interval (21-day or 28-day) ( $AUC_{tau}$ ) and other parameters may be derived.

This document is confidential.

### 9.2.2. IgG subclass levels

Blood samples for the analysis of IgG subclasses levels (IgG1, IgG2, IgG3, IgG4) will be taken before (as for all patients) and after the infusion 5 (28-day infusion schedule) or infusion 7 (21-day infusion schedule) at the time points indicated above in [Section 9.1](#).

The IgG subclass levels will be listed individually by time point, and serum concentration-time curve (individually and mean $\pm$ SD) will be plotted. The serum levels will be presented in g/L units.

### 9.2.3. PK parameters of specific IgG antibodies

Blood samples for the analysis of PK parameters for specific IgG antibodies (anti-Haemophilus influenza type b, anti-pneumococcal capsular polysaccharide, and anti-Tetanus toxoid) will be taken before and after the infusion 5 (28-day infusion schedule or infusion 7 (21-day infusion schedule) at the time-points indicated in [Section 9.1](#).

The specific antibodies levels will be listed individually by time point, and serum concentration-time curve (individually and mean $\pm$ SD) will be plotted. The serum levels will be presented in  $\mu$ g or IU/mL units.

Following PK parameters will be evaluated:

- $T_{1/2}$ ,  $AUC_{0-t}$ ,  $AUC_{0-inf}$ ,  $AUC_{\tau}$ ,  $V_d$ ,  $CL_{ss}$ ,  $C_{max}$ ,  $C_{min}$ ,  $T_{max}$ , and  $K_{el}$ ,  $C_{avg}$  and % Fluctuation.

$AUC_{0-inf}$  will be evaluated if data meet PK acceptance criteria to elimination parameters; AUC over dosing interval (21-day or 28-day) ( $AUC_{\tau}$ ) and other parameters may be derived.

## 9.3. Reliability of PK parameters

The following PK acceptance criteria will be applied to assess the reliability of the elimination parameters:

- 1.  $R^2_{adj}$  for the goodness of fit of the regression line through the data points must be  $\geq 0.80$ ;
- 2. The AUC extrapolation to infinity must be  $\leq 20\%$ .

For patients with unreliable  $K_{el}$  (criteria 1-2 are not met),  $K_{el}$ ,  $T_{1/2}$ ,  $AUC_{0-inf}$ ,  $CL_{ss}$  and  $V_d$  will be flagged in the individual data.

For patients with unreliable  $AUC_{0-inf}$  (only criterion 3 is not met),  $AUC_{0-inf}$ ,  $CL_{ss}$  and  $V_d$  will be listed and flagged in the individual data.

Flagged PK parameters will be excluded from summaries and statistical analyses.

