#### 4.4. Pharmacokinetic Endpoints

The following PK endpoints will be derived for the PK Evaluation Set only.

1. Serum total IgG levels, IgG subclasses levels and selected specific antibody levels before and after the 5th infusion (28-day infusion schedule) or 7th infusion (21-day infusion schedule).
2. PK parameters of total IgG before and after the 5th infusion (28-day infusion schedule) or 7th infusion (21-day infusion schedule).
3. PK parameters of specific IgG antibodies before and after the 5th infusion (28-day infusion schedule) or 7th infusion (21-day infusion schedule).
  - a. Anti-haemophilus influenza type b
  - b. Anti-tetanus toxoid
  - c. Anti-pneumococcal capsular polysaccharide
4. Plasma concentration-time curve,  $C_{max}$ ,  $T_{max}$ ,  $AUC_{0-t}$ , other parameters such as steady state parameters  $AUC_{tau}$ , average concentration of drug over the dosing interval ( $C_{ave}$ ), and steady state clearance ( $CL_{ss}$ ) may also be derived. Elimination parameters such as elimination rate constant, elimination half-life.  $AUC_{0-inf}$ , volume of distribution will be derived if data allow based on PK acceptance criteria.
5. Exploratory correlation analysis between health outcomes and PK parameters or trough concentrations may be included in the analysis.

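### SAP 9.3 flags PK parameters on an unlisted third criterion, leaves either/both open, and on its two most plausible readings drops steady-state clearance for AUC extrapolation above 20%, out of line with SAP 4.4

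*SAP*

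**What the plan says.** SAP 9.3 opens with "The following PK acceptance criteria will be applied to assess the reliability of the elimination parameters" and lists two: adjusted R² of the terminal fit at least 0.80, and a second beginning "The AUC extrapolation to infinity must be", with a limit of 20%. Two flag rules follow.

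- Unreliable Kel: Kel, T1/2, AUC0-inf, CLss and Vd are flagged where "criteria 1-2 are not met".
- Unreliable AUC0-inf: AUC0-inf, CLss and Vd are listed and flagged where "only criterion 3 is not met".

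The section closes: "Flagged PK parameters will be excluded from summaries and statistical analyses".

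SAP 4.4, with the same wording in protocol 10.4.4, sorts the parameters differently. AUCtau, average concentration "and steady state clearance" are steady-state parameters that may also be derived. A separate group begins "Elimination parameters such as elimination rate constant, elimination half-life" and ends, after AUC0-inf, with "volume of distribution will be derived if data allow based on PK acceptance criteria". SAP 9.2.1 and 9.2.3 list CLss among the parameters to be evaluated and make only AUC0-inf conditional on the acceptance criteria. No CLss formula appears in the unredacted text.

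**The concern.** A flag removes a value from the PK tables, so the wording of 9.3 decides what is reported. A programmer meets a criterion that does not exist, and a phrase that can mean that either criterion fails or that both do.

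Both rules also name CLss. By its usual definition, dose/AUCtau, CLss uses only the area within one dosing interval and needs no extrapolation to infinity. A limit on the extrapolated part of AUC0-inf therefore says nothing about its reliability. PK sampling stops at one dosing interval, so a long-lived IgG will often exceed that limit.

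Elimination at steady state in 20 adults is a stated PK objective (protocol 3.1, SAP 3.1.3), and SAP 9.4.4 summarises parameters separately by schedule. If CLss is kept only for patients who pass, its summary is smaller and also selective, because those who pass tend to have the shortest half-lives.

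**Working it through.** **Readings of 9.3**

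- A: failing either listed criterion flags all five parameters.
- B: criterion 3 means the extrapolation limit; failing it alone flags AUC0-inf, CLss and Vd.
- C: both listed criteria must fail and criterion 3 is void; extrapolation alone then flags nothing.

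C fits poorly with SAP 9.2.1 and 9.2.3, which evaluate AUC0-inf only if the criteria are met. Under A and B alike, extrapolation above 20% removes CLss. They differ on Kel and T1/2. The rule labels (unreliable Kel; unreliable AUC0-inf) favour B, which keeps both when only extrapolation fails.

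**Inputs from the documents.** The last PK sample is at day 28 (±2) or day 21 (±1), and the PK infusion is said to follow 5 half-lives (SAP 9.1). It falls at week 16 or week 18 (SAP 3.4). AUC uses the linear-up log-down method (SAP 9.2). The visible text gives no half-life and no extrapolated share, so there is no printed figure to reproduce.

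**Half-life ceiling implied by the plan.** 16 × 7 / 5 = 22.4 days on the 28-day schedule; 18 × 7 / 5 = 25.2 days on the 21-day schedule. For one product the smaller bound applies. It is an upper bound, not an expected value.

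**Extrapolated share, one-phase decline:** 2^(−tau/T1/2).

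| Half-life | 28-day | 21-day |
|---|---|---|
| 22.4 d | 2^(−1.25) = 42% | 2^(−0.9375) = 52% |
| 15 d (assumed) | 27% | 38% |
| 12 d (assumed) | 19.8% | 29.7% |

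**Half-life needed to pass.** 2^(−tau/T1/2) ≤ 0.20 gives T1/2 ≤ tau × ln 2 / ln 5: 12.1 days (28-day) and 9.0 days (21-day). An assumed wide distribution phase raises these to at most about 14.2 and 10.8 days.

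**Share of patients failing, closed form.** Assume a lognormal half-life with median 15 days and CV 30%, so log-SD = √ln(1.09) = 0.294. On the 28-day schedule, ln(12.06/15)/0.294 = −0.74, so 77% fail. On the 21-day schedule, ln(9.04/15)/0.294 = −1.72, so 96% fail.

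**Share failing, simulated.** Non-compartmental analysis was run on the SAP sampling times. Assumptions: half-life CV 20–30%, assay error 3–10%, distribution half-life about 2 days, and terminal slope from either the best adjusted-R² fit or the last three points (the visible SAP gives no rule).

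| Median half-life | 28-day | 21-day |
|---|---|---|
| 22.4 d | 96–100% | 99–100% |
| 15 d | about 67–81% | about 89–99% |
| 12 d | about 36–45% | about 71–86% |

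At 15 days, both criteria are met by 0.194–0.332 (28-day) or 0.014–0.092 (21-day) of patients. If all 20 evaluable adults were on one schedule, CLss would be summarised for about 4–7 or 0–2 of them. The real mix of schedules is not known.

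**How much the wording decides.** At 15 and 22.4 days, reading C flags at most about 10% of simulated patients, against 66–100% where either failure suffices.

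**The case against.** The strongest reply is that this is a numbering slip in a descriptive section. Much of it stands.

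- A reader might infer a flat contradiction between 9.3 and 4.4. The text does not go that far: 4.4 only permits CLss, and introduces the elimination group by example. The two sections disagree on which group CLss belongs to. Vd is conditional in both, so it is not in dispute.
- A reader might say that 9.3 contradicts its own opening sentence. It does not: that sentence neither lists the elimination parameters nor excludes clearance.
- A reader might conclude that Kel and T1/2 would also be lost for most patients. That holds only on reading A, the less likely one.
- Taken literally, reading C would leave CLss in. The passages against it, 9.2.1 and 9.2.3, speak of AUC0-inf and not CLss, so it is unlikely but not excluded.
- The 22.4-day ceiling is derived, not printed, and the failure rates rest on assumed half-lives and variability.
- Material between SAP 9.4.4 and 9.6 is redacted, so the lack of a CLss formula can be claimed for the visible text only.
- AUCtau and dose remain available, so CLss could be recovered for each patient.

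The slip reading does not rescue CLss, however. If criterion 3 is the extrapolation limit, CLss is still removed.

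**Conclusion.** The point holds. SAP 9.3 cannot be programmed without a guess, and on its two most plausible readings it excludes CLss on a test that the usual definition does not need, out of line with SAP 4.4 and protocol 10.4.4.

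The size depends on a half-life that the documents do not give. Nearly all patients fail near the implied ceiling and most fail at 15 days on either schedule. It would be too strong to say that few patients keep CLss whatever the half-life: at 12 days most on the 28-day schedule would pass, while most on the 21-day schedule would still fail. The one-phase thresholds of 12.1 and 9.0 days need no assumed half-life and apply to any analyte.

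The effect is confined to descriptive PK summaries. AUCtau, Cmax, Cmin, Cavg, troughs, individual listings, efficacy and safety are untouched. It should be fixed, but it does not threaten the trial's main conclusions.

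**What to change.** In SAP 9.3, correct the criterion number and give each criterion its own consequence:

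- Adjusted R² failure flags Kel, T1/2, AUC0-inf and Vd.
- Extrapolation failure flags AUC0-inf, and Vd if it is derived from AUC0-inf.

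Define CLss as dose/AUCtau and remove it from the extrapolation flag, so that 9.3 agrees with SAP 4.4 and protocol 10.4.4.

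State how AUCtau is completed when the last sample is early within its window. With one-phase decline at 22.4 days, the uncovered share of AUCtau is (2^(−26/22.4) − 2^(−28/22.4)) / (1 − 2^(−28/22.4)) = 4.6% for a sample 2 days early on the 28-day schedule. The same formula gives 3.4% for 1 day early on the 21-day schedule.

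Report the number of patients excluded for each parameter, by analyte and schedule.

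The cost is SAP wording and PK programming, with no new samples. If the interim PK report, planned after at least 20 patients, has already been produced under the present rule, its CLss table must be reconciled or re-run.
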